## LIST OF ABBREVIATIONS

ACCORD	Academic and Clinical Central Office for Research & Development - Joint office for University of Edinburgh and NHS Lothian
ABG	Arterial Blood Gas
AE	Adverse Event
ALI	Acute Lung Injury
ARDS	Adult Respiratory Distress Syndrome
AR	Adverse Reaction
CRF	Case Report Form
CRP	C Reactive Protein
CTA	Clinical Trials Authorisation
CXR	Chest X-Ray
DMSC	Data Monitoring and Safety Committee
DPFS	Developmental Pathway Funding Scheme
ECG	Electrocardiogram
ECRF	Edinburgh Clinical Research Facility
FBC	Full Blood Count
FC	Functional Capacity
FDG PET	Fludeoxyglucose Positron Emission Tomography
FEV1	Forced Expiratory Volume (1 second)
FiO2	Inspired Oxygen Concentration
GCP	Good Clinical Practice
ICH	International Conference on Harmonisation
HIV	Human Immunodeficiency Virus
HNE	Human Neutrophil Elastase
ICU	Intensive Care Unit
IMP	Investigational Medicinal Product
ISF	Investigator Site File
LFTs	Liver Function Tests
MHRA	Medicines Health Regulatory Authority
MI	Molecular Imaging
MRC	Medical Research Council
NAP	Neutrophil Activation Probe
PaO2	Partial Pressure of Arterial Oxygen
PCLE	Probe Based Confocal Endomicroscopy
PEEP	Positive End Expiratory Pressure
PISRC	Phase I/First-in-Human Study Review Committee

QP	Qualified Person
R&D	Research and Development
RIE	Royal Infirmary of Edinburgh
REC	Research Ethics Committee
RML	Right Middle Lobe
RLL	Right Lower Lobe
SAE	Serious Adverse Event
SpO2	Oxygen Saturations of pulsatile blood
SAR	Serious Adverse Reaction
SOP	Standard Operating Procedure
TOPS	The Over Volunteering Prevention System
SUSAR	Suspected Unexpected Serious Adverse Reaction
TMF	Trial Master File
TSE	Transmissible Spongiform Encephalopathy
UAR	Unexpected Adverse Reaction
U&Es	Urea and Electrolytes
VAP	Ventilator Associated Pneumonia
WGH	Western General Hospital

## LAY SUMMARY

Seriously ill patients may develop a complication called acute lung injury (ALI), a form of inflammation in which lung tissue is filled by fluid containing white blood cells called neutrophils. ALI is common and is often fatal (for example in the USA it is estimated that 190,000 patients develop ALI per annum, of whom 75,000 die). No pharmacological treatment has been shown to improve ALI.

Data from animal models and patients strongly suggest that neutrophils are central to disease progression. However no bedside methods exist to rapidly and accurately determine in seriously ill patients if neutrophils are present and if they are releasing damaging enzymes such as elastase. As such, the investigating team have developed and synthesised, to clinical grade, an imaging agent called NAP (Neutrophil Activation Probe). This detects activated neutrophils and also the damaging enzyme, human neutrophil elastase (HNE). We have extensively tested NAP in animal models for efficacy and safety. It reliably detects activated neutrophils and is not toxic.

NAP is a small molecule that is delivered in tiny doses (called microdoses) to areas of inflammation in human lungs through a bronchoscope. The activity of NAP is visualised by imaging through a tiny camera that is also introduced through the bronchoscope. This camera system is now widely used throughout the world in over 150 sites.

We therefore aim to test the utility and safety of NAP in an exploratory clinical study. The study involves the delivery of NAP to 6 healthy volunteers followed by delivering NAP to 3 patients in ICU with suspected ALI.

In the healthy volunteers study, healthy male volunteers recruited from the University of Edinburgh will be invited to participate.

In the ICU study, patients will be recruited from the ICU in the Royal Infirmary of Edinburgh (RIE) and the Western General Hospital (WGH), Edinburgh.

**If the study (which is supported by the Medical Research Council) demonstrates safety and also the ability to image activated neutrophils, we have secured further follow on funding to perform a clinical validation study.**

## PROFESSIONAL SUMMARY

Acute lung injury (ALI)/adult respiratory distress syndrome (ARDS) is clinically important (16% of mechanically ventilated patients acquire ALI, of whom one third die), yet no pharmacological therapy has been shown to impact significantly on outcome. This is in part due to inadequate stratification of patients with neutrophil predominant ALI/ARDS and the inability to determine disease activity and hence target therapy.

Molecular Imaging (MI) offers a potential strategy to visualize neutrophil activity *in vivo in situ*. Indeed FDG PET has been used to image neutrophil activity but it is not a bedside modality, and moving critically ill patients to remote scanners is dangerous and expensive and there are currently no bedside 'smart' MI solutions that can guide, at the cellular/functional level, the diagnostic or therapeutic pathway in patients with inflammatory lung disease. Indeed, in ICU, there is a specific need to rapidly diagnose patients with deteriorating gas exchange, particularly those with chest X-ray (CXR) shadowing. Such CXR infiltrates result from numerous causes including cardiac failure, fluid overload, secondary pneumonia and ALI/ARDS. All require different treatments but, at present, options to distinguish these conditions are severely limited, resulting in empirical 'blunderbuss' antimicrobial therapy and non-correction of the primary condition. There is now a pressing need to rapidly stratify such patients to inform focused implementation of specific targeted therapies.

Activated neutrophils and their histotoxic products, particularly human neutrophil elastase (HNE), have been specifically implicated in the pathogenesis of ALI/ARDS, and there is considerable clinical interest in new drugs in this area. However, there is currently no way of rapidly determining whether new therapeutic candidates are exerting their predicted effects *in situ* in the human lung prior to embarking upon major clinical trials. Such a solution would inevitably accelerate the pathway of new drugs to clinical application.

**The Proposed Solution:** probe-based confocal laser endomicroscopy (pCLE) combined with direct intra-pulmonary instillation of microdoses (pharmacologically-inactive and non-toxic) of a highly specific and sensitive 'smartprobe' (**NAP**) will detect neutrophil activity and the presence of active HNE in the lungs of ventilated ICU patients.

pCLE itself safely provides high-resolution, real-time images of the human lung at cellular resolution *in situ*. Alone, however, it provides no functional or molecular information. We have therefore embarked on a discovery programme to synthesise highly sensitive smartprobes, detectable by pCLE and specifically directed against key inflammatory events. This provides a new dimension of clinical application for this cutting-edge technology. **NAP**, the prototype has now been validated *in vitro* and *in vivo* where it is effective at a dose of <10µg and generates a powerful fluorescent signal in <30 sec. Our pilot study aims are to apply the combined utility of pCLE and **NAP** in healthy volunteers and patients with inflammatory lung disease. The study will also provide a prototypic foundation that can be applied to future smartprobes, not only in the lung but also in any organ accessible to endoscopy.

The primary end-point will be to visualise the delivery of a microdose of **NAP** in 6 healthy volunteers and 3 ICU patients. Demonstration of activated neutrophils by pCLE in ICU would be expected to lead directly to clinical validation trials in patients with ALI/ARDS.

# 1 INTRODUCTION

## 1.1 BACKGROUND

Critically ill patients commonly develop acute lung injury (ALI) characterised by accumulation of neutrophil polymorphs in the alveolar space with attendant fluid 'leak' across the alveolar-capillary membrane. The complication develops secondary to a wide range of primary pathologies, broadly classifiable into ALI secondary to pulmonary disease (e.g. pneumonia or aspiration of gastric contents) or extra-pulmonary disease (e.g. major extrathoracic trauma or sepsis). An American European Consensus Conference provided a pragmatic clinical definition for ALI fulfilled by,

- acute onset,
- the development of bilateral infiltrates on a frontal chest x-ray,
- impaired oxygenation (a PaO2:FiO2 ratio of ≤ 300mmHg) and
- the absence of left atrial hypertension (either on clinical grounds or by a measured pulmonary arterial wedge pressure of ≤18 mmHg).

A more severe form of ALI, adult respiratory distress syndrome (ARDS), fulfills the same criteria but requires a PaO2:FiO2 ratio of ≤ 200mmHg. ALI and ARDS therefore represent continua of the same clinical spectrum.

ALI is common and has a high mortality. For example, a comprehensive study in the USA estimated that 190,000 Americans develop ALI each year, approximately 74,000 of whom die. High rates of ALI have also been described in intensive care units (ICUs) in Europe and the UK. To place the clinical significance of ALI in context, it has been estimated that the mortality due to ALI is similar to that attributable to conditions such as human immunodeficiency virus (HIV), breast cancer or asthma. It is increasingly recognised that ALI/ARDS not only causes high mortality but consigns a high proportion of survivors to chronic morbidity and ill health.

Despite significant research efforts using a wide and logical range of drugs, no pharmacological treatment has yet been shown to impact significantly upon mortality from ALI/ARDS. Indeed the only medical intervention yet shown to influence mortality has been a 'protective' mechanical ventilation strategy. ALI therefore remains common, with an unacceptable associated mortality and morbidity. The lack of effective treatment may reflect the crucial role played by the blood neutrophil in the pathogenesis of ALI. Neutrophils are white blood cells, which are rapidly recruited to sites of inflammation during infection where they ingest and clear bacteria. In ALI this reaction appears inappropriate or over-exuberant and the neutrophil releases toxins which directly injure the lung. Reduction in neutrophil accumulation remains difficult to achieve by pharmacological means.

## 1.2 RATIONALE FOR STUDY

Our group has an interest in the factors regulating the recruitment of neutrophils to the inflamed lung. We have also had a long interest in imaging neutrophils. Recently a multidisciplinary collaboration has been formed with [name] in the Department of Chemistry to develop novel methodologies to image neutrophil activation. Funded by a MRC DPF award, we have generated a compound that is non-toxic and functional as an optical imaging agent to detect activated neutrophils. It is delivered as a microdose locally in the alveolar space and neutrophil activity imaged using pCLE. (A microdose is so small that it is not intended to produce any pharmacologic effect when administered to humans and therefore is also unlikely to cause an adverse reaction. For practical purposes this dose is defined as 1/100th of that anticipated to produce a pharmacological effect, or 100 micrograms, whichever is the smaller) It is envisaged NAP will be widely used in the future to detect neutrophil activity within the human lung in ICU to direct diagnostic and therapeutic decisions.

The tools and the expertise available locally, present a unique opportunity to assess the effectiveness and safety of delivering NAP to healthy volunteers and patients in ICU as a prelude to larger definitive clinical validation studies.

The study has 2 parts

Part A will evaluate the imaging parameters and safety of delivering NAP to 6 healthy volunteers within the MHRA accredited phase I unit at the Edinburgh Clinical Research Facility (ECRF)

In Part B we shall assess NAP delivery to 3 patients in ICU with suspected ALI/ARDS and pulmonary infiltrates at the RIE and WGH.

## 2 STUDY OBJECTIVES

### 2.1 OBJECTIVES

#### 2.1.1 Primary Objective

The primary objective is to deliver NAP as a microdose to 6 healthy volunteers and 3 patients in ICU and to test if **activated neutrophils within the alveolar space can be detected with NAP and pCLE over background autofluorescence**

#### 2.1.2 Secondary Objectives

The secondary objective is to deliver NAP and to observe if **NAP is non-toxic**.

### 2.2 ENDPOINT MEASURES FOR EXPLORATORY CLINICAL STUDY

#### 2.2.1 Primary Endpoint

- Visualise the delivery of a microdose of NAP in healthy volunteers and ICU patients.
- Delineate the presence of activated neutrophils within CXR infiltrates in ventilated patients with suspected ALI/VAP.

#### 2.2.2 Secondary Endpoints

Safety and tolerability as assessed by occurrence of adverse events (AEs) and serious adverse events (SAEs).

## 3 REGULATORY REQUIREMENTS

The protocol will be submitted to the REC for ethical approval. Local R&D Management and Edinburgh Clinical Research Facility (ECRF) phase I committee (PISRC) approval before the first participant is recruited. The study is 'First in Man' but the maximum dose level required is defined as a microdose within the relevant ICH M3(R2) guidelines. A CTA will be submitted to the MHRA.

## 4 STUDY DESIGN

The study is designed in 2 parts;

Part **A**) is a dose escalation in 6 healthy volunteers to deliver NAP and designed to assess the imaging parameters of NAP in the healthy lung and to monitor any unexpected serious adverse events (SAEs). No volunteer will be permitted to take part more than once.

Only if part A is successfully completed and the data monitoring and safety committee (DMSC) permit, part B will be undertaken. The REC will be informed of the outcome of part A and the DMSC decision to proceed.

Part **B**) is an exploratory clinical study in ICU to provide preliminary 'proof of concept' in 3 patients with suspected inflammatory lung disease.

#### 4.1 A) Delivery of NAP to healthy volunteers

Volunteers will return on a morning agreed after the screening medical described in Section 7.1 below. A brief history (pertaining to upper and lower respiratory tract symptoms) and respiratory examination will be repeated. Spirometry will be performed before proceeding.

For Volunteers, 1-4, they will be bronchoscoped and pCLE performed of the right middle lobe (RML). Immediately following this, NAP will be instilled via microcatheter into the RML and pCLE performed again of the RML.

Bronchoscopy will be performed using a standardised protocol and procedure employed throughout our work thus far. Briefly, local anaesthesia will be applied topically to the throat. Sedation with intravenous midazolam will be optional. Electrocardiogram (ECG) trace and SpO2 will be monitored continuously. A flexible fibreoptic bronchoscope will be passed per-orum or nasally and the bronchoscope wedged into the medial segment of the right middle lobe. The alveoflex will be passed down the working channel and alveoscopy performed with upto 4 transbronchial passes. Following this, the alveoflex will be withdrawn and a microcatheter passed into the medial segment of the RML and NAP instilled. Immediately following this pCLE will be performed as described above.

For volunteers, 5 and 6, they will be bronchoscoped and pCLE performed of the right lower lobe (RLL) and right middle lobe (RML). Immediately following this, NAP will be instilled via microcatheter into the RLL and RML and pCLE performed again of the RLL and RML. The dose of NAP will be divided between 2 segments in the RLL and one segment in the RML. The volunteer will receive a total of 80mcg (+/-20%) NAP.

Bronchoscopy will be performed using a standardized protocol and procedure employed throughout our work thus far. Briefly, local anesthesia will be applied topically to the throat. Sedation with intravenous midazolam will be optional. Electrocardiogram (ECG) trace and SpO2 will be monitored continuously. A flexible fibre-optic bronchoscope will be passed per-orum or nasally and the bronchoscope wedged into right lower and middle lobes. The alveoflex will be passed down the working channel and alveoscopy performed with upto 4 transbronchial passes per segment. Following this, the alveoflex will be withdrawn and a microcatheter passed into the RLL and RML and NAP instilled. Immediately following this pCLE will be performed as described above.

The volunteer will return to the ECRF after the procedure and will be monitored for a further 2 hours after which he can eat and drink. Volunteers will remain within the ECRF overnight. In the morning if, on assessment, volunteers observations are within acceptable parameters and they have a satisfactory cardio-respiratory examination, they will be discharged from the ECRF, with a number to contact should they feel unwell. The volunteers will be telephoned 3 days after dosing to enquire about any possible late unexpected adverse events.

6 volunteers will receive a dose escalation of NAP (below) on 6 separate days (each at least 6 days apart). After each episode, data will be submitted to the DMSC for approval to proceed to the next volunteer. The DMSC opinion will be documented and available to the ECRF prior to subsequent dosing events.

**Table 1**

Volunteer number	Dose of NAP (+/- 20%) (mcg)	Volume of NAP (mls)(80mcg/5mls)
1-2	5	0.312
3-4	10	0.625
5-6	80	5

Blood will be drawn just before bronchoscopy and delivery of NAP (t=0) and at t= 4 hours ( $\pm$ 30mins). For participants 5 and 6 an additional blood sample (less than 5 ml) will be collected

at t=1 hour ( $\pm$ 30 mins) for analysis to demonstrate the systemic uptake, or lack thereof, of the IMP. For participants 5 and 6, the first and second urine voiding following dosing will be collected for the same purpose. Spirometry will then be repeated 4 hours ( $\pm$ 30mins) after NAP delivery and the following morning. Bloods will be taken again in the morning. After each dosed volunteer has completed the 3-day follow up, clinical and laboratory data will be checked by the sponsor's representative prior to submission to the DMSC by the investigatory team. All data will be recorded on paper case report forms (CRFs). A summary of assessments and events is shown in table 2 below.

**Table 2**

	Day of screening	Study day on arrival	Following NAP delivery	1 hour after NAP delivery ( $\pm$ 30mins)	4 hours after NAP delivery ( $\pm$ 30 mins)	Overnight	24 hours ( $\pm$ 30 mins)
CXR	✓						✓
Cardiorespiratory examination	✓	✓			✓		✓
Bloods: FBC, U&Es, LFTs, CRP	✓	✓			✓		✓
Additional blood test for IMP level (Volunteers 5 and 6 only- non safety)				✓			
Spirometry	✓	✓			✓		✓
Informed consent	✓						
Urine collection for IMP level (non safety)			✓				
Observations, pulse, temperature, oxygen saturation	✓	✓	✓	✓	✓	✓	✓

#### **4.2 B) Delivery of NAP to 3 patients in ICU with pulmonary infiltrates**

ICU patients will be screened daily by ICU research nurses. If they fit the inclusion criteria described in Section 5.3, they or their personal/professional legal representative will be approached by a member of the research team to obtain consent. The attending consultant will also be approached and only after also gaining permission from the attending consultant will the patient be considered for inclusion into the study.

The pulmonary infiltrates will be identified on a CXR, which has been performed as part of routine clinical care and bronchoscopy and pCLE performed as above. A CXR will be performed immediately before the procedure. pCLE will be performed on areas without infiltrates as well as the affected segment/s. Following this, NAP will be instilled into the affected segment/s and unaffected segment/s via a microcatheter . A total of 80 mcg ( $\pm$ 20%) of NAP will be delivered

to the patient divided between the affected and unaffected segments. pCLE will be subsequently performed on the segments in which NAP has been delivered. We have performed bronchoscopy in over 70 patients in ICU over the last 5 years. The whole procedure including delivery of NAP will take approximately 30 minutes. The table below summarise the events and data to be collected before and after the procedure.

In addition, we intend to collect an additional sample (less than 5 ml) at  $t = 7.5$  mins ( $\pm 2.5$  mins) for analysis to demonstrate the systemic uptake, or lack thereof, of the IMP. For these participants, the urometer will be emptied at the time of bronchoscopy and then any urine passed over the next 2 hours will be collected to demonstrate the systemic uptake, or lack thereof, of the IMP.

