## **8 STUDY ASSESSMENTS**

### **8.1 OUTCOME MEASURES**

#### **8.1.1 Primary Outcome Measures**

This is an exploratory clinical study. The primary outcome measure is measurement of fluorescence and imaging parameters determined using pCLE and Cellvizio viewer software.

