##### **11.4.1.2 NAP delivery**

In part A, 5-80µg (+/- 20%) NAP will be delivered via a microcatheter instilled in the working channel of the bronchoscope. The exact time and dose delivered will be recorded. Delivery of fluorescein and other dyes have been reported with no recorded adverse effects.

Participants will be observed after NAP delivery and medications required to treat any adverse effects will be readily available (e.g. paracetamol in the event of significant symptoms of fever, salbutamol in the event of bronchospasm, oxygen in the event of hypoxia, adrenaline in the

event of anaphylaxis). The bronchoscopy suite and the ECRF are within the RIE and all resuscitation equipment and cardiac arrest teams are immediately to hand. Hence all the necessary facilities to safely undertake this procedure are available.

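### Does the open division of NAP between affected and unaffected segments in Part B spoil the fluorescence result?

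*Protocol*

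**What the plan says.** For Part B, Protocol section 4.2 sets a total of 80 mcg (±20%) per patient, "to the patient divided between the affected and unaffected segments". Both types are written as possibly plural: "NAP will be instilled into the affected segment/s and unaffected segment/s via a microcatheter". No number of segments and no shares are given. Imaging brackets the instillation. Beforehand, "pCLE will be performed on areas without infiltrates as well as the affected segment/s"; afterwards, "pCLE will be subsequently performed on the segments in which NAP has been delivered".

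For Part A, section 4.1 gives volunteers 5 and 6 the same total over a named set of segments: "The dose of NAP will be divided between 2 segments in the RLL and one segment in the RML". It does not state the shares either. Volunteers 1 to 4 receive 5 or 10 mcg in one segment of the middle lobe.

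Section 8.1.1 defines the outcome: "The primary outcome measure is measurement of fluorescence and imaging parameters determined using pCLE and Cellvizio viewer software". The primary objective (2.1.1) is to detect activated neutrophils above the lung's own autofluorescence. The endpoint specific to ventilated patients (2.2.1) is whether activated neutrophils are present inside the infiltrates seen on chest X-ray. On recording, section 11.4.1.2 says "The exact time and dose delivered will be recorded", in a paragraph that opens with Part A.

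**The concern.** Dosing and imaging both kinds of segment in the same patient makes the unaffected segment look like an internal control. If the signal depends on how much probe reaches a segment, that control is fair only when the amounts are comparable or known. The text guarantees neither. An affected segment could look brighter because it received more NAP, or a real difference could be hidden because it received less. With three patients, such an imbalance would not average out.

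There is a second worry. Part B may start only after Part A is successfully completed. If Part A spread 80 mcg over three segments and Part B uses two, the local amount in a patient could exceed anything seen in a volunteer, for imaging and for local tolerability alike.

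**Working it through.** **Inputs.** Total 80 mcg, with ±20% giving 64 to 96 mcg (4.1, 4.2, Table 1). Concentration 80 mcg in 5 mL, so 16 mcg/mL (7.1.1, Table 1). Part A top dose over 3 segments (4.1). Part B at least 1 affected plus 1 unaffected segment (4.2). The shares are not stated in either part and must be assumed.

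**The plan's own dose arithmetic.** Volume = dose / 16:
- 5/16 = 0.3125 mL (Table 1 prints 0.312)
- 10/16 = 0.625 mL
- 80/16 = 5 mL

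All three agree with Table 1.

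**Amount per segment under an equal split (assumed).** Amount = total / number of segments:

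| | Segments | At 80 mcg | Range at ±20% |
|---|---|---|---|
| Part A, volunteers 5-6 | 3 | 26.7 | 21.3 to 32.0 |
| Part B | 2 | 40.0 | 32.0 to 48.0 |
| Part B | 3 | 26.7 | 21.3 to 32.0 |
| Part B | 4 | 20.0 | 16.0 to 24.0 |

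The two-segment case is 40/26.7 = 1.5 times Part A. With three segments the excess is nil, and with four Part B is lower. If Part A was not split equally, one volunteer segment received more than 26.7 mcg and the excess shrinks.

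**Affected-to-unaffected ratio.** With *a* affected and *u* unaffected segments and half the total given to each type (assumed), the amounts are 40/*a* and 40/*u*, so the ratio is *u*/*a*:
- 1 + 1: 40 v 40 mcg, ratio 1.0
- 1 + 2: 40 v 20 mcg, ratio 2.0
- 1 + 3: 40 v 13.3 mcg, ratio 3.0
- 2 + 1: 20 v 40 mcg, ratio 0.5
- 3 + 1: 13.3 v 40 mcg, ratio 0.33

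With the total divided evenly over all dosed segments, each receives 80/(*a* + *u*) and the ratio is 1.0 for every *a* and *u*. Section 4.2 speaks of division between segments, so this reading is at least as natural as half to each type.

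**What the ratios do not show.** They are ratios of amount, not of fluorescence. Turning one into a bias needs an amount-to-signal relation, and the protocol gives none. It does give two facts that bear on it. Section 7.1.1 says the signal arises on contact with neutrophils or elastase, so on the protocol's own account extra probe without its target should not by itself produce it. The Professional Summary reports that NAP worked at under 10 µg in preclinical testing. The smallest amount listed above, 13.3 mcg, is 40/3; at the lower tolerance it is (64/2)/3 = 10.7 mcg, still above that level. Neither fact proves that human signal is independent of amount, but neither supports reading a 2- or 3-fold amount as a 2- or 3-fold bias.

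**What the stated objective needs.** Detection above autofluorescence compares a segment after NAP with background. Section 4.2 has affected and unaffected areas imaged before instillation, so the background reference for an infiltrate comes from that infiltrate and does not depend on what another segment received.

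**The case for a change.** The strongest case for a change is that later analysis cannot recover an amount that was never written down. The recording sentence in 11.4.1.2 sits in a Part A paragraph and mentions no segments, and Table 3, which lists the Part B assessments, has no row for the dose delivered. A pre-NAP image removes background but does not make the post-NAP signal independent of the amount instilled. The protocol itself escalates the dose in Part A partly to study imaging, which suggests that amount matters. A sentence and a case report form field per segment would cost little.

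Part of this stands. The split is unstated, and an informal comparison of affected with unaffected segments would be easier to read with the amounts beside it. But that comparison is implied by the procedure; no objective or endpoint names it. The recording sentence does not exclude Part B, and the case report form, where amounts per segment would normally be entered, is not among the documents, so their absence is not established.

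The Part A argument is weaker. The protocol frames its microdose limit per person (1.2, 7.1.1), and that total is the same in both parts, as is the concentration. Nothing requires Part A to cover an amount per segment, and the safety committee must agree to proceed after each dosed participant (11.2). Sections 4.1 and 4.2 describe different people and different anatomy; they do not contradict each other. Requiring equal amounts in compared segments would come close to writing a dosing rule, which is not a statistical matter, and the site and extent of infiltrates will differ between patients.

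**Conclusion.** No change is called for. Section 4.2 leaves out a detail; it does not state a rule that gives a wrong result. The possible imbalance is 0.33- to 3-fold in amount under the plans listed, but only if half the total goes to each type and the segment counts differ. The possible excess over Part A is 1.5-fold, but only with exactly two equally dosed segments in Part B and equal thirds in Part A. Under an even division the imbalance is nil. No size can be put on any fluorescence bias, because the protocol gives no amount-to-signal relation.

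The stated primary question has its own pre-NAP reference and survives any of these splits. This rests on two assumptions: that the bedside team divides the instillations sensibly and logs them, and that any affected-versus-unaffected contrast is reported descriptively, as suits three patients in an exploratory study.
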